5.10. Criteria for Study or Site Termination

Throughout the course of the study, new information may become available to the Sponsor, its designee, or regulatory authorities indicating that the study or a study site should be terminated. Such decisions will be made after consultation between the Sponsor or its designee and the Investigator. The Sponsor or its designee has the right to terminate the participation of an individual site or the entire study at any time, for any reason, which may include:

- The incidence or severity of AEs in this study or other studies indicate a potential safety hazard to patients
- Unsatisfactory patient enrollment
- Inadequate data recording
- Non-adherence to protocol or applicable regulatory guidelines in study conduct.

6. SELECTION AND WITHDRAWAL OF PATIENTS

Patients will be male and non-pregnant female volunteers between 12 and 65 years of age inclusive (Phase 2) and between 8 and 65 years of age (Phase 3) at Screening with a genetically confirmed diagnosis of PWS, able to understand and provide written consent or assent, and who meet all the inclusion and none of the exclusion criteria. Eligibility for this study will be confirmed during the Screening and Tolerability Periods.

6.1. Patient Inclusion Criteria

To be eligible for this study, patients must meet all of the following inclusion criteria:

1. Presence of a parent/legal guardian that is able to consent for their participation. Parent/caregiver/legal guardian can complete the required assessments throughout the study. Patient consent/assent will be obtained if the patient is 8 years of age or older and has the mental capacity to understand and sign a written consent/assent form and/or give verbal assent
2. Males and females between:
 - a. Phase 2: 12 and 65 years of age (inclusive) at time of consent/assent
 - b. Phase 3: 8 and 65 years of age (inclusive) at time of consent/assent
3. Documentation of genetically confirmed PWS diagnosis
4. If a caregiver helps in completing the HQ-CT or other questionnaires, the same caregiver is available to complete the questionnaire throughout the duration of the study
5. If female, is either not of childbearing potential (defined as premenarchal or surgically sterile [bilateral tubal ligation, bilateral oophorectomy, or hysterectomy]) or practicing one of the following medically acceptable methods of birth control up to 4 weeks after the last dose of RAD011 or placebo:
 - a. Double barrier method (i.e., condom plus occlusive cap (diaphragm or cervical/vault caps), condom or occlusive cap plus spermicide),

- b. Hormonal methods such as oral, implantable, injectable, vaginal ring, or transdermal contraceptives at a stable dose for a minimum of 1 full cycle (based on the patient's usual menstrual cycle period) before IP administration
- c. Intrauterine device (IUD) or intrauterine hormone-releasing system (IUS)
- d. If not using hormonal contraceptives or IUD or IUS, then all male partners throughout the study must have been vasectomized and have received medical assessment of the surgical success

- 6. If male, is vasectomized and has received medical assessment of the surgical success or agrees to use an approved method of contraception (double barrier method as described in [Inclusion Criterion 5](#), female partner's use of an IUD or IUS [in place at least 12 weeks prior to dosing], oral contraceptives or female partner who is surgically sterile or 2 years postmenopausal) and agrees to use this method for 4 weeks after last administration of RAD011 or placebo
- 7. If receiving growth hormone (GH), psychotropic therapy, metabolic treatments that could affect appetite (including metformin), and other treatment including thyroid hormone, must be on the same medication and stable dose for at least 90 days prior to consent/assent
- 8. Any non-medical interventions (e.g., counseling, behavior modification) should be stable for at least 90 days prior to consent/assent
- 9. HQ-CT eligibility automatically calculated in the electronic data capture (EDC) system:
 - a. Visit 2
 - i. Patients with a mean HQ-CT score ≥ 13 (from Visit 1 and Visit 2) will be eligible to continue in the Tolerability Period
 - b. Visit 5
 - i. Patients with a mean HQ-CT score ≥ 13 (from Visit 3, Visit 4 and Visit 5) will be eligible for randomization, and
 - ii. Patients with a decrease in HQ-CT score (from Tolerability Period to the Screening Period) ≤ 7 will be eligible for randomization

6.2. Patient Exclusion Criteria

Patients meeting any of the following criteria will be excluded from the study:

- 1. Hypersensitivity or intolerance to CBD, or any other excipients used in the RAD011 preparation
- 2. Known use of cannabis or cannabinoid containing products (including topical products) within 90 days prior to consent/assent
- 3. History of chronic liver disease, such as cirrhosis or chronic hepatitis due to any cause
- 4. Positive urine test for drugs of abuse, including tetrahydrocannabinol (THC), or known history of drug, alcohol, or substance abuse
- 5. Use of prescription or over-the-counter weight loss agents within 90 days prior to consent/assent
- 6. Implementation of new food restrictions or environmental restrictions within 90 days of consent/assent

7. Any significant comorbid condition or disease:
 - a. Respiratory disease, heart disease, or psychiatric disorder which in the opinion of the Investigator would preclude the patient from participating or
 - b. Uncontrolled type 1 or type 2 diabetes as determined by the Investigator or
 - c. Clinically significant ECG abnormalities or other evidence of clinically significant heart disease as determined by the Investigator or
 - d. Uncontrolled sleep apnea as determined by the Investigator or
 - e. Neutropenia with neutrophil counts <1,000 /microL (grade 3 or grade 4 neutropenia as defined by CTCAE v5.0) or
 - f. History or presence of gastrointestinal disorders or any other condition known to interfere with the absorption, distribution, metabolism, or excretion of drugs taken orally as determined by the Investigator
8. QT interval corrected for heart rate (HR) according to Fridericia's formula (QTcF) meeting the following criteria:
 - a. For males and females aged 8 to <20 years: QTcF >439 msec
 - b. For males aged 20 to 65 years: QTcF >450 msec
 - c. For females aged 20 to 65 years: QTcF >470 msec
9. At consent/assent, patients with age-matched hypertensive levels of systolic and/or diastolic blood pressure may be excluded at the Investigator's discretion if deemed to be in the best interest of the patient.
10. Pregnant (determined by a positive serum pregnancy test) or lactating female
11. Unwillingness or inability to follow the procedures outlined in the protocol
12. Estimated glomerular filtration rate <30 mL/min/1.73m² or protein/creatinine ratio ≥0.4
13. Bilirubin >1.5 × upper limit of normal (ULN), or aspartate aminotransferase (AST), alanine aminotransferase (ALT) >3 × ULN, or international normalized ratio (INR) >1.5 × ULN
14. Patient judged by the Investigator or Sponsor (or designee) as unable to comply with the treatment protocol, including appropriate supportive care, follow up, and research tests
15. Other genetic, hormonal, chromosomal, cognitive, or behavioral impairment
16. If living in a group home, patient spends less than 25 waking hours with their caregiver per week.
17. Significant risk of committing suicide based on history, routine psychiatric examination, or based on the Investigator's judgment
18. Participation in any other study involving an investigational product or device within 4 weeks or 5 half-lives (whichever is longer) of consent/assent or longer as required by local regulations

6.3. Patient Withdrawal Criteria

A patient is free to withdraw consent/assent and/or discontinue participation in the study at any time, for any reason, without prejudice to further treatment. A patient may also be withdrawn from the study at any time at the discretion of the Investigator.

6.3.1. Discontinuation of Investigational Product

The IP may be prematurely discontinued by the patient or the Investigator for reasons including, but not limited to:

- Patient's inability to comply with protocol requirements
- The IP is no longer in the patient's best interest, at the Investigator's discretion
- Patient's decision to discontinue the IP
- Discontinuation due to patient becoming pregnant
- An unexpected, related SAE, or a SUSAR
- Requirement for prohibited concomitant medication ([Section 7.2](#)).

Patients who discontinue IP but do not withdraw consent/assent will continue to be followed according to the planned Schedule of Assessments but will not undergo drug dispensing or drug accountability. Patients who are unwilling or unable to complete planned assessments should undergo the End of Study Visit Assessments (Visit 14, Week 34).

Patients who discontinue IP may have their IP tapered over up to 14 days, at the Investigator's discretion.

6.3.2. Drug-Induced Liver Injury

Increase of serum alanine aminotransferase (ALT), aspartate aminotransferase (AST), alkaline phosphatase (ALP), or total bilirubin to $>3 \times$ ULN should be followed by repeat testing within 48 to 72 hours of awareness of the increase, of ALT, AST, ALP, and total bilirubin to confirm the abnormalities and to determine if they are increasing or decreasing. Repeat laboratory testing can be done locally and/or centrally depending on clinical availability and turnaround time for prompt evaluation. There also should be an inquiry made about the symptoms. Repeat laboratory testing should also be done centrally as soon as possible, if not already tested centrally within 48-72 hours of awareness of the increase.

It is critical to initiate close observation immediately upon detection and confirmation of early signals of possible drug-induced liver injury, and not to wait until the next scheduled visit or monitoring interval. If additional testing, beyond that specified in the study protocol, is carried out, it is important that the patient's information be added to the case report forms and database.

Close observation includes:

- Repeating liver enzyme and serum bilirubin tests two or three times weekly. Frequency of retesting can decrease to once a week or less if abnormalities stabilize or the IP has been discontinued and the patient is asymptomatic;
- Obtaining a more detailed history of symptoms and prior or concurrent diseases;
- Obtaining a history of concomitant drug use (including nonprescription medications and herbal and dietary supplement preparations), alcohol use, recreational drug use, and special diets;

- Ruling out acute viral hepatitis types A, B, C, D, and E; autoimmune or alcoholic hepatitis; nonalcoholic steatohepatitis; hypoxic/ischemic hepatopathy; and biliary tract disease;
- Obtaining a history of exposure to environmental chemical agents;
- Obtaining additional tests to evaluate liver function, as appropriate (e.g., international normalized ratio, direct bilirubin);
- Considering gastroenterology or hepatology consultations.

Discontinuation of IP should be considered if:

- ALT or AST $>8 \times$ ULN;
- ALT or AST $>5 \times$ ULN for more than 2 weeks;
- ALT or AST $>3 \times$ ULN **and** (total bilirubin $>2 \times$ ULN **or** international normalized ratio >1.5);
- ALT or AST $>3 \times$ ULN with the appearance of fatigue, nausea, vomiting, right upper quadrant pain or tenderness, fever, rash, and/or eosinophilia ($>5\%$).

All study patients showing possible drug-induced liver injury should be followed until all abnormalities return to normal or to the baseline state. Drug-induced liver injury may develop or progress even after the causative drug has been stopped. Results should be recorded in the electronic case report form (eCRF) and in the database. Note that longer follow-up can sometimes reveal an off-drug repetition of what had appeared to be drug-induced liver injury, indicating that liver injury was related to underlying liver disease.

All potential cases of drug-induced liver injury should be reviewed with the Medical Monitor. The IP should be discontinued at the Investigator's discretion and the Sponsor notified at the earliest convenience.

6.3.3. Patient Withdrawal

The Investigator should withdraw the patient from the study if they believe that participation is no longer in the patient's best interest, or in the event of study termination by the Sponsor. If the patient elects to withdraw from the study, reason(s) for withdrawal should be documented. The Investigator will discuss with the patient procedures for withdrawal and any additional care or treatment alternatives available at that time. In addition, patients unable to tolerate the 0.1 mL/kg/day dose level during the Tolerability Period or their assigned dose level(s) during the Dose Escalation Period will be withdrawn from the study.

If a patient withdraws consent/assent from the study, the patient should be encouraged to complete all End of Study Visit assessments (Visit 14, Week 34) completed as described in the Schedule of Assessments ([Table 7](#)). At time of withdrawal of consent/assent, the patient will be withdrawn from all additional study procedures and follow-up.

Data collected until patient withdrawal will be retained and included in the analysis of the study in accordance with local rules and regulations.

6.3.4. Lost to Follow-Up

A patient will be considered lost to follow-up if they repeatedly fail to return for scheduled visits and are unable to be contacted by the study site.

The following actions must be taken if a patient fails to return to the clinic for a required study visit:

- Attempt to contact the patient and reschedule the missed visit(s) as soon as possible and counsel the patient on the importance of maintaining the assigned visit schedule
- Make every effort to regain contact with the patient (where possible, 3 telephone calls and, if necessary, a certified letter to the patient's last known mailing address) and document these efforts in the patient's medical record
- Ascertain if the patient wishes to and/or should continue in the study
- Consider the patient lost to follow-up once the aforementioned steps have been taken, contact with the patient has not been regained and document the reason for loss to follow-up if known.

6.4. Evaluation of Eligibility at the End of the Screening and Tolerability Periods

6.4.1. Screening Period

During the Screening Period, Investigators will have to review a patient's eligibility to proceed to the Tolerability Period. This will include review of inclusion/exclusion criteria, laboratory assessments, a review of PWS diagnosis, and ECG reading.

In addition, at the end of the Screening Period (Visit 2) and prior to initiating dosing of patients at Visit 2, patients/caregivers must first complete the HQ-CT.

The EDC system will automatically calculate a mean HQ-CT score from Visit 1 and Visit 2. Patients must have a mean HQ-CT score ≥ 13 to be eligible to continue in the Tolerability Period. Patients with a mean score < 13 will not be eligible to continue in the Tolerability Period and will be discontinued from the study.

6.4.2. Tolerability Period

At the end of the Tolerability Period (Visit 5), Investigators will review a patient's eligibility to be randomized and proceed to the Dose Escalation Period.

Patients/caregivers must first complete the HQ-CT. The EDC system will automatically calculate a mean HQ-CT score from Visit 3, Visit 4 and Visit 5. Patients must have a mean HQ-CT score ≥ 13 to be eligible to be randomized and proceed to the Dose Escalation Period. Patients with a mean score < 13 will not be eligible for randomization and will not have the opportunity to participate in the long-term extension study (SCOUT-016).

In addition, the EDC system will also automatically calculate the change in HQ-CT score from the Tolerability Period to the Screening Period. This change is calculated as:

$$\text{Mean HQ-CT score (Visit 3, Visit 4, Visit 5)} - \text{Mean HQ-CT score (Visit 1, Visit 2)}$$

Patients with a decrease HQ-CT score ≤ 7 will be eligible for randomization. Patients with a decrease in HQ-CT score > 7 will not be eligible for randomization and unable to proceed to the Dose Escalation Period.

7. TREATMENT OF PATIENTS

7.1. Investigational Product Administration

The IP (RAD011 or placebo) will be administered orally twice daily with food, approximately 12 hours apart. Patients must take the IP with food throughout the study.

When patients are seen at the research site, dosing should be performed at the research site at the time points indicated in [Table 7](#), during the Visit 2 and Visit 5 assessments. The dose prior to Visit 8 (Week 10) should be taken approximately 4 to 6 hours prior to the visit to allow for PK collection approximately 6 ± 2 hours after the dose ([Section 10.1.14](#)). When patients have a remote visit, dosing does not need to be performed at the research site.

7.1.1. Tapering of Investigational Product for Patients Entering the Taper and Follow-Up Periods

For patients not participating in the long-term extension study (SCOUT-016) and entering the Taper and Follow-Up Periods, the IP will be tapered over 14 days. Following completion of Visit 14 (End of Study/Week 34 Visit), the IP should be decreased by 50% during the first 7 days, followed by an additional 50% taper during the following 7 days and then discontinued. The taper schedule may be modified at the discretion of the Investigator but cannot occur over a longer time than 14 days. A final safety follow-up will be conducted 14 days after the IP is discontinued for patients who do not elect to continue into the long-term extension study.

7.2. Concomitant Medications

Growth hormone, psychotropic medications, and other therapies such as thyroid hormones (including homeopathic or naturally sourced thyroid supplements), started prior to enrollment and at stable doses for at least 90 days prior to enrollment are permitted in this study. Doses of psychotropic medications, thyroid hormones, and GH may be adjusted during the study if clinically required, at the discretion of the Investigator. However, change in such medications must be documented in the EDC.

7.2.1. RAD011 Drug-Drug Interactions Overview

The major biotransformation pathway for CBD is similar to that of other cannabinoids and is mediated by hydroxylation by CYP enzymes. Its interactions with human drug metabolizing enzymes (as a substrate, inhibitor, or inducer) were recently reviewed ([Forster, 2021](#)). Cannabidiol is metabolized primarily in the liver by CYP3A4 and to a lesser extent by CYP2C19. Specifically, CBD inhibits CYP3A4, CYP3A5, and CYP1A1 in vitro. It also appears to inhibit CYP2C9 and the transport protein P-glycoprotein. Thus, Cannabidiol may inhibit these two isozymes (CYP3A4 and CYP 2C19), as well as having small effects on CYP3A5, CYP2D6, CYP1A1, CYP1A2, and CYP2C9 (see Investigator's Brochure for more information).

Medications that are strong inhibitors/inducers/sensitive substrates with a narrow therapeutic index for those CYP enzymes, although not prohibited, may require that the patient is monitored with special care to identify any AEs arising due to the potential for altered drug metabolism. Thus, the Investigator and study center staff should monitor patients who are taking concomitant medications that are metabolized by CYP3A4/5, CYP2C19, CYP1A1/2, CYP2C8/9, CYP2D6, or by P-glycoprotein with special care.

Patients who experience adverse events due to significant drug/ drug interactions may have treatment discontinued while remaining on the study, at the Investigator's discretion.

7.3. RAD011 Precautions

The following precautions should be communicated to patients or observed during the course of the study:

- Somnolence and sedation: monitor for somnolence and sedation and advise patients not to drive or operate machinery until they have gained sufficient experience on RAD011. Concomitant use of RAD011 with other central nervous system depressants (including alcohol) may increase the risk of sedation and somnolence
- Hypersensitivity reactions: advise patients to seek immediate medical care. Discontinue and do not restart RAD011 if hypersensitivity occurs.
- Withdrawal of antiepileptic drugs: should be gradually withdrawn to minimize the risk of increased seizure frequency and status epilepticus.

7.4. Treatment Adherence

Importance of adherence to regimen will be reviewed with patients and study staff should ensure that patients remain compliant with the IP and study assessments. In addition, drug accountability will be completed at each study visit as detailed in the Pharmacy Manual.

7.5. Randomization and Blinding

Randomization will occur at Visit 5 (Week 7) after review of all eligibility criteria by the Investigator.

Both Investigators and patients will be blinded to the randomization assigned treatment. During the Tolerability Period, all patients will receive 0.1 mL/kg/day of placebo. To maintain the blind, multiple placebo groups were created to mimic the RAD011 groups: low volume (0.1 mL/kg/day), mid volume (0.2 mL/kg/day), and high volume (0.4 mL/kg/day). During the dose escalation period, the volume of blinded therapy for the mid volume and high volume placebo groups will increase in the same manner as the mid dose and high dose RAD001 groups, further ensuring blinding between RAD011 and placebo.

The matching (appearance, smell and taste) placebo and RAD011 product will utilize the same MCT vehicle.

Phase 2 of the study

Patients who meet eligibility criteria will be randomized in a 2:2:2:1:1:1 manner to receive double-blind treatment with IP, defined as either low dose (10 mg/kg/day, [0.1 mL/kg/day])

RAD011, mid dose (20 mg/kg/day, [0.2 mL/kg/day]) RAD011, high dose (40 mg/kg/day [0.4 mL/kg/day]) RAD011, low volume (0.1 mL/kg/day) placebo, mid volume (0.2 mL/kg/day) placebo, or high volume (0.4 mL/kg/day) placebo using a centralized randomization system. Randomization will be stratified according to current use of GH treatment (yes/no) and age (≥ 16 or < 16 years old).

Phase 3 of the study

Following review by the DMC (Section 10.4), 1 or 2 dose levels will be recommended for continued development and assessment in Phase 3 of the study. Therefore, following the Tolerability Period, patients meeting randomization eligibility criteria will be randomized using a centralized randomization system in a way to obtain a balanced number of patients on RAD011 and placebo to receive double-blind treatment with IP at dose levels recommended by the DMC.

If 1 dose is recommended for continued development and assessment in Phase 3 of the study, randomization will be 1:1 (RAD011: placebo).

If 2 doses are recommended for continued development and assessment in the Phase 3 part of the study, randomization will be 2:2:1:1 (RAD011 dose 1: RAD011 dose 2: placebo: placebo).

Patients aged 8 to < 12 years may be allowed to participate in the Phase 3 part of the study and will be randomized in a way to obtain a balanced number of patients on RAD011 (at dose levels recommended by the DMC) and placebo.

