5. INVESTIGATIONAL PLAN

5.1. Overall Study Design

This is a seamless Phase 2/3, double-blind, randomized, placebo-controlled clinical study in patients diagnosed with PWS. Following consent (or legal guardian consent and patient assent as appropriate), patients will be screened for eligibility to participate in this study.

The Phase 2 portion of the study is to assess safety and tolerability. Dose safety and tolerability decisions will be made in Phase 2. All patients randomized to placebo and to the selected dose level(s) for Phase 3 evaluation will be included in the Phase 3 efficacy evaluation.

The study will consist of the following six similar periods for Phase 2 and Phase 3 of the study:

1. Screening Period (3 weeks)
 - a. Review of eligibility prior to proceeding to the Tolerability Period
2. Tolerability Period (6 weeks)

- a. Determination of randomization eligibility[†]
3. Dose Escalation Period (3 weeks)
4. Maintenance Period (24 weeks)[‡]
5. Taper Period (2 weeks)[‡]
6. Follow-Up Period (2 weeks)[‡].

[†]Patients who do not meet criteria for randomization eligibility will not be randomized to study SCOUT-015.

[‡]All patients participating in the Maintenance Period may be offered participation in the long-term extension study (SCOUT-016). Patients who do not enroll in the SCOUT-016 study will have their IP tapered over 2 weeks (14 days), followed by a 2-week (14-day) safety follow-up.

After approximately 45 patients complete 4 weeks of the Maintenance Period of the Phase 2 part of the study, the Data Monitoring Committee (DMC) will meet to review safety and tolerability data and to recommend 1 or 2 RAD011 dose level(s) for evaluation in the Phase 3 part of the study. Details regarding the dose selection for the Phase 3 part of the study will be described in the DMC charter.

A schematic overview of the study is presented in [Figure 2](#) for the Phase 2 part, and in [Figure 3](#) for the Phase 3 part.

Screening Period (3 weeks, Visit 1 [Weeks -3 to 0])

Phase 2 and Phase 3 of the study

All patients with a signed informed consent/assent will undergo Screening assessments. Screening assessments will include a full medical history and physical exam, a review of documentation of PWS diagnosis, an ECG, laboratory assessments, and questionnaires (including the HQ-CT) as described in [Section 5.8.2](#). To be eligible for the Tolerability Period, patients must meet the following criterion:

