Abbreviations: DMC = Data Monitoring Committee; FU = follow-up; LTE = long-term extension; RAND = randomization.

*Patients assigned to placebo will include low, mid, and high volume placebo to match active drug and will be combined for statistical analysis.

Figure 3: Study Design Schematic – Phase 3 of the Study

Abbreviations: FU = follow-up; LTE = long-term extension; RAND = randomization; TBD = to be determined.

* Patients assigned to placebo will be further broken down to achieve balanced exposure between placebo and RAD011 patients. Patients in the placebo group (matching volume) will be combined for statistical analysis.

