11.4. Statistical Analyses

11.4.1. Populations for Analyses

The following patient populations will be defined for analysis:

- Safety Population: the Safety Population will include all randomized patients who were treated with at least one dose of IP

- Intent to Treat (ITT) Population: the ITT Population will include all randomized patients
- Modified ITT (mITT) Population: the mITT Population will include all patients aged ≥ 12 years who were randomized, received at least 1 dose of IP, had at least 1 post-randomization HQ-CT questionnaire completed, and were randomized to receive the dose level(s) recommended for development in Phase 3 of the study, including patients in the Phase 2 part of the study who received the chosen dose level(s)
- Per Protocol (PP) Population: the PP Population will include all patients aged ≥ 12 years who were randomized, received at least 1 dose of IP, completed Week 34 without significant protocol deviations that were prospectively defined to impact efficacy (see SAP) and received the dose level(s) recommended for development in Phase 3 of the study, including patients in Phase 2 of the study who received the chosen dose level(s)
- Pharmacokinetic Evaluable Population: the PK Evaluable Population will include all patients who received at least 1 dose of IP and underwent at least 1 PK sample collection.

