11.4.2. Primary Endpoint

The primary endpoint, change in HQCT score from Baseline to End of Study (Week 34) will be analyzed for the mITT population based on the treatment policy estimand using a mixed model for repeated measures (MMRM) with change in HQCT score as the response variable and randomization assignment, Baseline HQ-CT score and stratification variables (age [≥ 16 or < 16 years] at randomization and GH treatment at randomization [yes/no]) and time \times treatment interaction as fixed effects. Patient will be included as a random effect with an unstructured covariance matrix. A multiple imputation will be used for missing data. Baseline will be defined as the mean HQ-CT score (Visit 1, Visit 2).

For the primary endpoint analysis at Week 34, multiple imputation will be used to assign a value to those cases with missing data. The full conditional specification method with predictive means matching as described in Berglund & Heeringa ([Berglund, 2014](#)) will be used. This method uses all of a patient's known primary outcome measures at Baseline, Weeks 10, 19, 27, and/or 34 weeks to impute any missing values for Week 34.

DMC Recommendation of two RAD011 Doses

The primary comparison will be mean change in HQ-CT as calculated via least square means comparing RAD011 low dose vs. placebo and RAD011 high dose vs. placebo at Week 34. Low dose and high dose groups will be compared to placebo at the two-sided 0.025 level so overall type 1 error is maintained at two-sided 0.05 level.

DMC Recommendation of one RAD011 Dose

The primary comparison will be mean change in HQ-CT as calculated via least square means comparing RAD011 vs. placebo at Week 34. RAD011 will be compared to placebo at the two-sided 0.05 level.

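### The primary model pools Phase 2 and Phase 3 without a stage term although the dose-to-placebo ratio can change between them, so a small part (about 7%) of any between-stage drift can enter the treatment contrast

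*Protocol*

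**What the plan says.** **Allocation (Section 7.5).** In Phase 2, "Patients who meet eligibility criteria will be randomized in a 2:2:2:1:1:1 manner to receive double-blind treatment with IP", that is, three doses and three matching placebo volumes. In Phase 3 with two doses, "randomization will be 2:2:1:1 (RAD011 dose 1: RAD011 dose 2: placebo: placebo"; with one dose, "randomization will be 1:1 (RAD011: placebo".

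**Pooling.** Section 5.1: "All patients randomized to placebo and to the selected dose level(s) for Phase 3 evaluation will be included in the Phase 3 efficacy evaluation". The footnote to Figure 2 adds: "Patients assigned to placebo will include low, mid, and high volume placebo to match active drug and will be combined for statistical analysis". The mITT definition in Section 11.4.1 is worded differently. It requires that patients "were randomized to receive the dose level(s) recommended for development in Phase 3 of the study", and does not say what happens to Phase 2 placebo of a volume that is not carried forward.

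**Sample size (Section 11.1).** 15 Phase 2 patients (two doses) or 30 (one dose) are added on top of the efficacy set as belonging to dose levels not selected. In the two-dose case only the low and high placebo volumes are described as combined.

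**Model (Section 11.4.2 and Synopsis).** The fixed effects are "randomization assignment, Baseline HQ-CT score and stratification variables" (age group and GH use), plus time by treatment. No term identifies the stage in which a patient was randomized. Section 11.4.3 carries the same approach over to continuous secondary and other endpoints.

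**The concern.** When the allocation ratio differs between two stages and the stages are pooled, stage becomes associated with treatment. If mean HQ-CT change also differs between stages, a model without stage attributes part of that difference to treatment. The model adjusts for both stratification factors but not for the variable that sets the allocation probability.

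Some drift is credible from the protocol itself. The endpoint is reported by patients or caregivers, and Section 5.2 notes variability in HQ-CT response and expects a placebo effect that wanes. Recruitment runs over successive calendar periods. In the one-dose case a patient's chance of active drug falls from 2/3 in Phase 2 to 1/2 in Phase 3, which could alter expectation. At stake are a small bias in the primary estimate, in either direction, and a small loss of control over type I error.

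**Working it through.** **The plan's own figures.** Section 11.1 assumes 50 per group, difference 5, SD 7. SE = 7 x sqrt(2/50) = 1.40, and 5/1.40 = 3.571.
- Two-sided 0.025: Phi(3.571 - 2.241) = 0.908 (0.900 by noncentral t). Stated: 90%.
- Two-sided 0.05: Phi(3.571 - 1.960) = 0.946 (0.943 by noncentral t). Stated: 94%.
- 15% dropout: 150/0.85 = 176.5 and 100/0.85 = 117.6. Stated: 176 and 118. Section 11.1 also gives about 180 for the first; 176 is used here because it matches the Synopsis and the total of 191.

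**Inputs.** Phase 2 size: 45, the approximate number at the DMC review (Section 10.4), taken as 10/10/10 active and 5/5/5 placebo. Phase 3 arms: the rest of 176 or 118, split equally. Drift: not given in the protocol; 2-5 points is an assumption.

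**Formulas.**
- Leakage = Phase 2 share of the active arm minus Phase 2 share of the placebo arm.
- Bias b = leakage x drift.
- SE = 7 x sqrt(1/(0.85 n1) + 1/(0.85 n0)).
- Two-sided alpha = Phi(-z + b/SE) + Phi(-z - b/SE).

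**Two doses, all Phase 2 placebo kept.** Phase 3 arms: (176 - 35)/3 = 47. Shares: 10/57 = 17.5% and 15/62 = 24.2%. Leakage is 6.6% in size, and SE = 1.393.

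**One dose, all placebo kept.** Phase 3 arms: (118 - 25)/2 = 46.5. Shares: 10/56.5 = 17.7% and 15/61.5 = 24.4%. Leakage is 6.7%, and SE = 1.399.

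**Two doses, matched placebo only.** Phase 2 is 10:10, Phase 3 is 1:1. Leakage is 0.

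**One dose, matched placebo only.** Phase 2 is 10:5. Phase 3 arms: (118 - 15)/2 = 51.5. Shares: 10/61.5 = 16.3% and 5/56.5 = 8.8%. Leakage is 7.4% with the opposite sign.

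| Case | Phase 2 ratio, one dose to placebo | Leakage | Bias at drift 2 / 5 | Alpha at drift 2 / 5 |
|---|---|---|---|---|
| Two doses, all placebo | 2:3 | -6.6% | 0.13 / 0.33 | 0.026 / 0.029 |
| Two doses, matched only | 1:1 | 0 | 0 / 0 | 0.025 / 0.025 |
| One dose, all placebo | 2:3 | -6.7% | 0.13 / 0.33 | 0.051 / 0.057 |
| One dose, matched only | 2:1 | +7.4% | 0.15 / 0.37 | 0.051 / 0.058 |

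Bias is shown as absolute size. The Phase 3 ratio is 1:1 in every row.

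**Larger Phase 2.** If the 15 patients per dropped dose in Section 11.1 are all active, Phase 2 is 3 x 15 + 22.5 = 67.5. With all placebo kept, the shares are 15/56.2 against 22.5/63.7 (two doses) and 15/55.25 against 22.5/62.75 (one dose). Leakage is 8.6-8.7%. A 5-point drift then gives a bias of 0.43-0.44 and alpha of 0.032 or 0.061.

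**Which reading do the counts fit?** With 45 patients, each dose level holds 45/3 = 15, that is, 10 active and 5 matched placebo. The 15 and 30 set aside therefore fit dropping the unmatched placebo, against the wording of Section 5.1.

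**Cost of adjusting.** Stage-adjusted variance at Week 34 = 49 / sum over stages of n1 n0/(n1 + n0). For two doses with all placebo, after dropout: 8.5 x 12.75/21.25 + 39.95 x 39.95/79.9 = 5.10 + 19.98 = 25.08. SE = 1.398, against 1.393 unadjusted. Power moves from 91.1% to 90.9%. For one dose it moves from 94.7% to 94.5% (all placebo) or 94.4% (matched only).

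**The case against.** The best defence is that the imbalance is not certain. On the matched-placebo reading, which the mITT wording and the 15/30 counts support, the two-dose ratio is 1:1 in both stages and nothing leaks. This stands, and it means a reader should not infer that placebo always holds the larger Phase 2 share: that is true only if all placebo is kept, and it reverses in the one-dose, matched-only case. Nor does the overall active-to-placebo ratio change in the two-dose case; it is 2:1 in both stages. What can shift is the per-dose comparison, which is the one tested.

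It is also fair that the effect is small. A reader might infer that between-stage drift passes straight into the result, but more than 90% of it does not. The upper drift used here equals the whole 5-point design effect, and no figure in the protocol supports it. The larger Phase 2 is likewise an inference from Section 11.1. The protocol does not say that sites differ by stage. Blinding, run-in and HQ-CT entry criteria are common to both stages, and patients under 12 are outside the mITT population.

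Finally, Section 11 leaves detail to the SAP, which is not at hand. But the covariates of the primary model are already listed in the protocol, so this is more than a detail left open. None of these arguments covers every case: the explicit text of Section 5.1, and the one-dose case on either reading, leave stage associated with treatment.

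**Conclusion.** The point holds as a minor, conditional flaw. In three of the four combinations of dose number and placebo set, stage is associated with treatment and the model does not adjust for it. About 6.6-7.4% of an additive drift then leaks with 45 Phase 2 patients, in a direction that depends on the placebo set and on the sign of the drift. A drift of 2-5 points moves the estimate by less than 0.4 points. Even a drift of 7 points, one full SD, gives 0.47 points in the two-dose, all-placebo case (alpha 0.033; power 84.5% if the bias runs against the drug).

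The documents do not support the stronger conclusion that the primary result is unreliable: at plausible drifts a true 5-point effect would not be overturned. The figures rest on 45 Phase 2 patients, equal Phase 3 arms, SD 7, 15% dropout in each arm, a normal approximation and a drift common to both arms. Since the repair costs almost nothing, it is a free improvement.

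**What to change.** 1. Add stage (randomized in Phase 2 or Phase 3) and stage by visit as fixed effects in the primary MMRM, in Section 11.4.2 and the Synopsis. The interaction is needed because the contrast is at Week 34, and a stage main effect alone removes only a drift that is the same at every visit.
2. Do the same in the analogous models for secondary and other endpoints (Section 11.4.3), and include stage in the imputation model.
3. State which Phase 2 placebo patients enter the mITT population, and bring Section 5.1, the Figure 2 footnote, Section 11.1 and Section 11.4.1 into line.

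The cost is a few lines of text before unblinding, a few degrees of freedom and at most about 0.3 points of power. No new data and no extra patients are needed.
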